1.5 Compliance Statement

The investigators will perform the study in accordance with this protocol, will obtain consent and assent, and will report unanticipated problems involving risks to subjects or others in accordance with IRB Policies and Procedures and all federal requirements. Collection, recording, and reporting of data will be accurate and will ensure the privacy, health, and welfare of research subjects during and after the study.

2 STUDY OBJECTIVES

2.1 Primary Objective (or Aim)

The primary objective of this study is to determine whether 6.67 to 33.33 hours of BioStream Training improves the performance of children with ASD on social skills assessments including in comparison to an alternate game. Specifically with respect to the following:

The mean change from baseline score on the following assessments based on post-final game play session assessment compared to the alternate game group:

- a. Subject gaze patterns as measured by video eye tracking assessment.
- b. Subject gaze patterns as measured by the dyadic interaction task.
- c. Mean change in baseline score on the Ekman 60 Faces Test.
- d. Mean change in baseline score on the TOVA.
- e. Mean change in baseline score on the SRS.

2.2 Secondary Objectives (or Aim)

The secondary objectives are to observe changes in subject gaze patterns during additional social skills assessments after engaging in BioStream Training, including in comparison to an alternate game.

Specifically with respect to the following:

The mean change from baseline score on the following assessments based on post-final game play session assessment compared to the alternate game group:

- a. Subject gaze patterns as measured on the videos of emotional expression assessment.
- b. Subject responses to the CJARS survey.

3 INVESTIGATIONAL PLAN

3.1 General Schema of Study Design

This protocol is a comparison group controlled trial of a computer-based social skills training intervention. The BioStream Training is being compared to a modified version of the BioStream Training, which will not include the same therapeutic exercises or any video game that is rated E (Everyone) by the Entertainment Software Rating Board. The game will be played by subjects in the non-intervention group for the same length of playing time and at the same frequency, as the BioStream Training intervention group. It will require a similar game controller device as that which is used by the intervention group and will be computer based.

3.1.1 Initial Screening

Potential subjects will be first screened by any study team member in an in-person or telephone interview with the parent/guardian. After written informed consent is obtained to the initial screening (in the case of an in-person interview) or verbal informed consent is obtained to the initial screening (in the case of a telephone interview), protocol inclusion and exclusion criteria will be reviewed with the parent/guardian. The parent/guardian will also be asked for a list of the medications the subject is currently taking and that information will be recorded. A subset of questions from the SRS will be asked as part of the screening. The parent/guardian will also be asked if the subject has a diagnosis of ADHD and if so, that will be noted.

Prospective Study Participant Initial Screening Form. This short questionnaire will be administered to the parent/guardian in-person or by telephone prior to the study visit to

query their children's video game playing habits. This questionnaire should take less than 15 minutes to complete. Questions related to the inclusion/exclusion criteria will also be asked to determine eligibility.

3.1.2 Phase I Visit 1

Parental/guardian permission (informed consent) and, if applicable, child assent, will be obtained. Subjects will participate in social skills assessments. The subject will participate in the Peabody Picture Vocabulary Test, 4th Edition [34]. If the study team member determines that the subject's intelligence standard score is below 40, then the subject will not be able to continue to be included in the study per the exclusion criteria (see page 4). The subject will participate in the Ekman 60 Faces Test. If the subject score is greater than 75% correct, then the subject will not be able to continue to be included in the study per the exclusion criteria.

Additionally, to confirm certain inclusion criteria, the parent/guardian will be required to present the study team member with a note from a licensed medical professional indicating the subject has been diagnosed with ASD and also if the subject has been diagnosed with ADHD. The study team member will inspect the note, but will not take possession of it. The study team member will provide training to the parent/guardian (in the case of in-home use) or the teacher (in the case of in school use) or the therapist (in the case of therapy center use) regarding use of the Subject Computer, and review the protocol for the subject's training or use of the alternate game (as applicable).

3.1.3 BioStream Training Group

The BioStream Training group will undergo an estimated 40-60 minute training session on how to use the BioStream Training game. Further details on further assessments conducted during the visits can be found in section 4.2.

3.1.4 Alternate Game Group

The alternate game group will undergo an estimated 40-60 minute training session on how to use the alternate game on the first visit. Otherwise, their visits will be exactly the same as the BioStream Training Group. Further details on further assessments conducted during the visits can be found in section 4.2

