| Study Phases | 
Phase I
 
 • Initial Screening • Visit 1 – Informed Consent, Ekman 60 Faces Test, PPVT • Visit 2 – Assessments and Surveys (Baseline) • Week 1 (following Visit 2) – Gameplay – daily transmission of game data • Week 1 – Survey – data transmission • Visit 3 – Assessments and Surveys • Week 2 – Gameplay – daily transmission of game data • Week 2 – Survey – data transmission • Visit 4 – Assessments and Surveys • Week 3 – Gameplay – daily transmission of game data • Week 3 – Survey – data transmission • Visit 5 – Assessments and Surveys • Week 4 – Gameplay – daily transmission of game data • Week 4 – Survey – data transmission • Visit 6 – Assessments and Surveys 
(Note: Phase II may not begin immediately following phase I)
 
Phase II
 
 • Week 1 – Gameplay – daily transmission of game data • Week 1 – Survey – data transmission • Visit 1 – Assessments and Surveys |

| | |
|--------------------------------------|--|
| | 
 • Week 2 – Gameplay – daily transmission of game data • Week 2 – Survey – data transmission • Visit 2 – Assessments and Surveys • Week 3 – Gameplay – daily transmission of game data • Week 3 – Survey – data transmission • Visit 3 – Assessments and Surveys • Week 4 – Gameplay– daily transmission of game data • Week 4 – Survey – data transmission • Visit 4 – Assessments and Surveys |
| Efficacy Evaluations | 
The primary efficacy endpoints will be:
 
The mean change from baseline score on the following assessments based on post-final game play session assessment compared to the alternate game group:
 
 a. Subject gaze patterns as measured by video eye tracking assessment. b. Subject gaze patterns as measured by the dyadic interaction task. c. Mean change in baseline score on the Ekman 60 Faces Test. d. Mean change in baseline score on the TOVA. e. Mean change in baseline score on the SRS. 
Secondary endpoints:
 
The mean change from baseline score on the following assessments based on post-final game play session assessment compared to the alternate game group:
 
 a. Subject gaze patterns as measured on the videos of emotional expression assessment. b. Subject responses to the CJARS survey. |
| Pharmacokinetic Evaluations | N/A |

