All written or electronic forms (except Informed Consent Forms and Assent Forms) will employ a unique alphanumeric identifier; in no case will the participant's name or other identifying information appear on these forms. The user ID for the BioStream Training and alternate game shall use the same unique alphanumeric identifier. The study team will accomplish this on all parent/guardian or teacher or therapist questionnaires (as applicable) which have lines for child and parent name by applying a label with unique alphanumeric identifier and instructing parents/guardians or teacher or therapists to use generic labels (e.g., biological mother) rather than writing their names. The PI will keep a master list containing PHI and subject ID number separate from coded data forms, which will be maintained in a locked file drawer, cabinet, or lock box in the PI's office. Only the PI will have access to this location. The master list will be maintained on a separate password-protected computer and be stored in an encrypted password protected file. Video recordings will stored on password-protected and/or encrypted data storage devices including computers, external hard drives, and/or flash drives only accessible by members of the study team.

**TABLE 1: SCHEDULE OF STUDY PROCEDURES
(INITIAL SCREENING)**

| | Estimated time | Parent or subject? |
|---|-----------------------|---------------------------|
| Informed Consent | 15 minutes | Parent |
| Review of Inclusion/Exclusion Criteria (Initial Screening Interview) | 15 minutes | Parent |
| Video Game Interview Form (Parent-Report) | 15 minutes | Parent |

**TABLE 2: PHASE I SCHEDULE OF STUDY PROCEDURES
(HOME, SCHOOL, THERAPY CENTER, OR RESEARCH ORGANIZATION)**

| | Estimated time (total over all visits) | Parent or subject? | Visits applicable (Total 6 Visits) |
|--|---|---------------------------|---|
| Informed Consent/Assent (if applicable) | 30 minutes | Parent and subject | Visit 1 |

| | | | |
|---|----------------------------------|----------------|--|
| Peabody Picture Vocabulary Test (PPVT) | 20 minutes | Subject | Visit 1 |
| Ekman 60 Faces Test | 10 minutes | Subject | Visit 1 |
| SRS (Parent-Report) | 50 minutes | Parent | Visits 2-6 |
| C-JARS (Parent-Report) | 50 minutes | Parent | Visits 2-6 |
| Dyadic Interaction Task | 50 minutes | Subject | Visits 2-6 |
| Eye Tracking Video Assessment | 50 minutes | Subject | Visits 2-6 |
| Ekman 60 Faces Test | 50 minutes | Subject | Visits 2-6 |

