| Emotional Expression Video Assessment | 50 minutes | Subject | Visits 2-6 |
| TOVA | 109 minutes | Subject | Visits 2-6 |
| Game and equipment introduction (if applicable) | 40-60 minutes | Parent | Visit 1 |
| BioStream Training | 6.67-33.33 hours | Subject | Over a period of 28 days following Visit 2 |
| Weekly Parental/Teacher/Therapist Survey | 20 minutes | Parent | 1 survey/per week |
| Subject Interview/Survey (if applicable) | 40 minutes | Subject | Visits 3 - 6 |
| Parent/Teacher/Therapist Interview/Survey (if applicable) | 40 minutes | Parent | Visits 3 - 6 |
| Equipment return (if applicable) | 5 minutes | Parent | Visit 6 |
| TOTAL | 13.48 hours – 41.15 hours | Subject | |
| TOTAL | ~4.25 hours* | Parent | *Excludes time spent for oversight of subject during BioStream Training |

**TABLE 3: PHASE II SCHEDULE OF STUDY PROCEDURES
(HOME, SCHOOL, THERAPY CENTER, OR RESEARCH ORGANIZATION)**

| | Estimated time (total over all visits) | Parent or subject? | Visits applicable (Total 4 Visits) |
|---------------------------------------|---|---------------------------|---|
| SRS (Parent-Report) | 40 minutes | Parent | All Visits |
| C-JARS (Parent-Report) | 40 minutes | Parent | All Visits |
| Dyadic Interaction Task | 40 minutes | Subject | All Visits |
| Eye Tracking Video Assessment | 40 minutes | Subject | All Visits |
| Ekman 60 Faces Test | 40 minutes | Subject | All Visits |
| Emotional Expression Video Assessment | 40 minutes | Subject | All Visits |
| TOVA | 87 minutes | Subject | All Visits |
| BioStream Training | 6.67-33.33 hours | Subject | Over a period of 28 |

| | | | |
|---|----------------------------------|----------------|--|
| | | | days |
| Weekly Parental/Teacher/Therapist Survey | 20 minutes | Parent | 1 survey/per week |
| Subject Interview/Survey (if applicable) | 40 minutes | Subject | All Visits |
| Parent/Teacher/Therapist Interview/Survey (if applicable) | 40 minutes | Parent | All Visits |
| Equipment return (if applicable). | 5 minutes | Parent | Visit 4 |
| TOTAL | 11.45 hours – 38.12 hours | Subject | |
| TOTAL | ~2.5 hours* | Parent | *Excludes time spent for oversight of subject during BioStream Training |

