4.2 In-Person Study Visits

During the in-person study visits, parents and subjects will complete the following assessments, described in section 1.4 unless otherwise noted. Tables 1 and 2 also show details on the schedule of all in-person assessments for both phases.

Social Responsiveness Scale – Parent (SRS) – 10 minutes, parent only (may be administered by phone).

Childhood Joint Attention Rating Scale (C-JARS) – 10 minutes, parent only (may be administered by phone).

Dyadic Interaction Task – 10 minutes, subject only.

Eye Tracking Video Assessment – 10 minutes, subject only.

Ekman 60 Faces Test – 10 minutes, subject only.

Emotional Expression Video Assessment – 10 minutes, subject only.

Test of Variables of Attention (TOVA) – 22 minutes, subject only.

An introduction to game and equipment (Only Phase I Visit 1) – 40 – 60 minutes, with the parent/guardian, teacher, or therapist.

Subject Interview/Survey (described in section 5.4.1) – 10 minutes, subject only.

Parent/Teacher/Therapist Interview/Survey (described in section 5.4.2) – 10 minutes, parent, teacher, or therapist only.

Video Recording of Study Visits: All study team member visits to the home, school, or therapy center may be video recorded using a single or multiple video cameras and tripods.

Please note that for subjects who are using the BioStream Training in their school, therapy center or research organization, their parent/guardian only needs to be present for the first visit. After that visit, surveys involving the parent including the Social Responsiveness Scale and Childhood Joint Attention Rating Scale can be conducted over the phone.

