5.7.2 Efficacy Analysis

The primary analysis will be based on all subjects randomized at the initial visit for who initial visit and final visit data is collected.

Paired-sample t-tests will be used to measure changes from baseline within each group, and independent sample t-tests will be used to measure changes from baseline relative to the alternate game group for all endpoints.

For all endpoints, we will determine whether there were statistically significant changes in scores from baseline or relative to the alternate game group. Significance will be set at $p < 0.05$. Multiplicity of primary endpoints will be managed via statistical corrections.

Secondary endpoints will be evaluated in a similar manner. Analysis will include all subjects for who initial visit and final visit data is collected. The treatment and control groups will be compared using t-tests as described above.

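### Randomisation and the arm-specific game introduction come before the Visit 2 baseline, so the baseline parent-rated SRS and C-JARS are scored after allocation

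*Combined protocol and SAP*

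**What the plan says.** - **Randomisation.** Section 5.7.2 bases the primary analysis on "all subjects randomized at the initial visit" who also have initial-visit and final-visit data.
- **Game introduction.** Section 3.1.4 gives the control arm a "training session on how to use the alternate game on the first visit". Table 2 covers both arms: "Game and equipment introduction (if applicable) | 40-60 minutes | Parent | Visit 1". Section 4.2 likewise confines the introduction to Phase I Visit 1.
- **Content and audience.** Under section 3.1.2 the Visit 1 session is specific to the arm: staff "review the protocol for the subject's training or use of the alternate game (as applicable"). The person trained is the parent for home use, the teacher for school use and the therapist for therapy-center use. No trainee is named for research organizations.
- **Baseline.** The synopsis lists "Visit 2 – Assessments and Surveys (Baseline"). Table 2 has "SRS (Parent-Report) | 50 minutes | Parent | Visits 2-6", and C-JARS follows the same schedule. Neither is scheduled at Visit 1.
- **Play.** Table 2 starts game play after Visit 2.
- **Masking.** Section 3.2 has blinding in its title but describes none. The only masking stated anywhere is for the annotators of the dyadic-task video (sections 1.1, 1.4 and 7.3).
- **Analysis.** Sections 5.5 and 5.7.2 compare change from baseline between arms by independent-sample t-test at 0.05. The Supplement to Statistical Analysis Plan adds a 2×2 mixed ANOVA for the Ekman, SRS and C-JARS.

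**The concern.** A baseline should be fixed before anyone whose judgement feeds into it knows the allocation. Here the order is reversed for the two parent-rated scales. A parent who has just been taken through the assigned game may rate the child differently at Visit 2, for example from hope or disappointment. If that affects the arms unequally and then fades, it enters the between-arm difference in change and looks like a treatment effect, or hides one.

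There is also a loss problem. A child who leaves between Visits 1 and 2 has been randomised but has no baseline for eye tracking, the dyadic task, TOVA, SRS, the emotional-expression videos or C-JARS. Only the Ekman test is also given at Visit 1, as an eligibility test. Such a child cannot contribute a change score on the other measures, and the loss occurs after allocation.

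**Working it through.** **1. Is the parent counted as attending the introduction?** Table 2 gives about 4.25 hours of parent time in Phase I. The parent rows, in minutes, are consent 30, SRS 50, C-JARS 50, weekly survey 20, interview 40 and equipment return 5, which sum to 195.

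- Without the introduction: 195/60 = 3.25 h
- With 40 minutes: 235/60 = 3.92 h
- With 60 minutes: 255/60 = 4.25 h

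The stated total is reproduced only with a full 60-minute introduction, so the schedule counts the parent as present for it.

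**2. Order of events.** Visit 1: randomisation and arm-specific introduction. Visit 2: first SRS and C-JARS. After Visit 2: play. No earlier parent rating exists to serve as baseline.

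**3. What a baseline rating shift would do.** The documents give no size for the shift, so a range is shown. Assumptions, none of them in the documents:

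- 75 per arm (150 split equally) and a two-sided test at 0.05
- no true effect
- equal SDs at baseline and final visit, with correlation r
- a shift δ (in SD units) in one arm, present at baseline and absent at the final visit

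SD of change = √(2(1−r)). SE of the difference = SD of change × √(2/75). False-positive rate = P(|Z + δ/SE| > 1.96).

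For r = 0.7: SD of change = √0.6 = 0.775, and SE = 0.775 × 0.163 = 0.126. For δ = 0.2, δ/SE = 1.58 and the rate is 35%.

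| r | SE | δ = 0.1 | δ = 0.2 | δ = 0.3 |
|---|---|---|---|---|
| 0.5 | 0.163 | 9% | 23% | 45% |
| 0.7 | 0.126 | 12% | 35% | 66% |
| 0.8 | 0.103 | 16% | 49% | 83% |

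The plan does not name its multiplicity correction. If it were Bonferroni over five primaries (0.05/5 = 0.01), the r = 0.7 row would be 4%, 16% and 42%.

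**4. Would another analysis remove it?** The Time × Condition test in the supplement's mixed ANOVA is equivalent to the change-score t-test, so the same rates apply. Adjusting for baseline carries r × δ instead of δ, with SE = √(1−r²) × √(2/75). At r = 0.7 the SE is 0.714 × 0.163 = 0.117, and the rates are about 9%, 22% and 44%. That is a partial reduction, because the covariate is itself affected by allocation.

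**5. Persistent shift.** If the same shift δ is present at both visits, the change difference is δ − δ = 0 and the error rate stays at 5%.

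**The case against.** The strongest counter-argument is that the same parent, with the same knowledge, rates at both visits, so a stable bias cancels in a change score. That is correct. The table above applies only to a shift that has gone by the final visit, and nothing in the documents says how a parent's rating would move over four weeks. The figures show sensitivity and do not predict an effect.

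Parent knowledge is also less than certain for some children. In schools and therapy centers the teacher or therapist is trained. The parent attends Visit 1 (section 4.2) and the introduction is booked as parent time, but the text does not say that the parent learns the assignment. The control may be a modified version of the same product (sections 1.2 and 3.1), so knowing which game was assigned need not mean recognising it as the control.

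A reader might infer three stronger points that the documents do not support:

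- **Equipment is handed over at Visit 1.** Table 2 schedules an introduction. Section 5.4.2 describes the hand-over without dating it.
- **Children may play before baseline.** Play is scheduled only after Visit 2, and section 1.2 provides for recording game usage.
- **Rating bias affects every primary endpoint.** Only the SRS is parent-rated. Eye tracking and TOVA are instrument-recorded, dyadic video is annotated by masked raters, and the Ekman is a test the child takes.

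What remains is the visit order itself, the absence of any pre-allocation parent rating, and the post-randomisation loss.

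**Conclusion.** The concern holds in a limited form. The order of events is well documented: allocation and arm-specific training come before the baseline. Rating bias can reach one of five primary endpoints (SRS) and one secondary (C-JARS). It is explicit for home use, and likely but unstated for school and center use. For the remaining endpoints the issue is confined to a baseline taken after allocation and children randomised without one; the Ekman is partly protected by its Visit 1 administration.

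The effect on error rates cannot be computed from the documents. It ranges from none, if the shift persists unchanged, to the rates tabulated, if it fades entirely. Its direction is unknown, so it could equally mask a real benefit. It would be wrong to conclude that a baseline shift always passes in full into the result, because that needs a shift that disappears by the final visit. This should be corrected because the remedy is cheap, not because a particular bias has been shown.

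**What to change.** In sections 3.1.2 to 3.1.4, 4.2 and Table 2, keep consent and the PPVT and Ekman eligibility tests at Visit 1. Move randomisation and the game and equipment introduction to the end of Visit 2, after every baseline assessment is complete. Amend section 5.7.2 to say that subjects are randomised after the Visit 2 baseline. For school, center and research-organization subjects, obtain the parent SRS and C-JARS before allocation is disclosed, either in person at Visit 1 while the parent is present or by telephone before the end of Visit 2. Section 4.2 already allows the telephone route.

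The cost is 40-60 minutes moved from Visit 1 to Visit 2 and some telephone coordination. No visit is added and the start of play does not change.

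The change does not cure unmasked final ratings. With a clean baseline, a parent bias that persisted would no longer cancel, so unmasked final SRS and C-JARS ratings should be stated as a limitation.

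The enrolment period in section 3.3.1 ended in February 2020 and the supplement is dated April 2022. If conduct is complete, report Visit 2 SRS and C-JARS by arm, report by arm the number randomised without a Visit 2 baseline, and state that the baseline followed allocation.

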3.2 Allocation to Treatment Groups and Blinding

Subjects will be randomly assigned to one of the two groups (BioStream Training group, or alternate game group) as an ongoing process throughout enrollment.

